### **Plans to Minimize Risk:**

## **DMXB-A**

The subject care protocol protects subjects against risk by ensuring that they see an investigator biweekly for pill counts and pill dispensing. At each visit, the side effects questionnaire and Columbia Suicide Severity Rating Scale will be completed. The subject is evaluated further for any adverse event, with a physical exam if indicated. A comprehensive metabolic panel will be repeated at screening and at weeks 4, 8 and 12, to assess liver function. CBC, TSH and A1c tests will be completed at screening. A lipid panel will be completed at screening and week 12. Women will complete pregnancy tests at screening, baseline, and monthly throughout the study (weeks 4, 8, and 12).

Criteria for a subject to continue in the study will include the ability to attend biweekly appointments. Subjects who cannot comply or who express desire to leave the study because of diminished tolerability will be withdrawn. The stopping criteria are well defined. Specifically, any laboratory or vital sign value that is over five standard deviations from the mean, or a significant abnormality on physical exam, will lead to discontinuation of that subject. Changes over two times normal in laboratory values will be followed up immediately with repeat assessment. If the change persists, the subject will be stopped. An increase of serum transaminases to  $> 3x$  ULN will be followed by repeat testing of ALT, AST, ALP, and TBL within 48 to 72 hours. If repeat testing still shows levels  $> 3x$  ULN, close observation will be initiated to determine whether abnormalities are improving or worsening. This threshold was chosen as per the stated guidelines in the FDA Guidance for Industry Drug-Induced Liver Injury: Premarketing Clinical Evaluation, which suggest  $> 3x$  ULN as a reasonable threshold, as lesser elevations are common and nonspecific. If close monitoring is not possible, the subject will discontinue the drug and stop the study. Close observation will include repeating liver enzyme and bilirubin tests 2 times per week. Frequency of retesting can decrease to one per week or less if abnormalities stabilize. In addition, close monitoring will include obtaining a more detailed history of prior or concurrent diseases, repeated administration of the concomitant medications questionnaire, obtaining a history of exposure to environmental chemical agents, and ruling out acute viral hepatitis types A, B, C, D, and E, autoimmune or alcoholic hepatitis, and cardiovascular disease. As per the Guidance for Industry Drug-Induced Liver Injury, the subject will discontinue the drug and stop the study if any of the following criteria are determined:

- ALT or AST  $> 8x$ ULN
- ALT or AST  $> 5x$ ULN for more than 2 weeks
- ALT or AST  $> 3x$ ULN and (TBL  $> 2x$ ULN or INR  $> 1.5$ )
- ALT or AST  $> 3x$ ULN with the appearance of fatigue, nausea, vomiting, right upper quadrant pain or tenderness, fever, rash, and or eosinophilia ( $> 5\%$ )

During close observation in the event of potential liver effects, we will also evaluate data for alternative causes. If elevated levels persist, we will rule out acute viral hepatitis (via serological markers), alcoholic and autoimmune hepatitis (via history, physical examination, and serologic testing), cardiovascular causes (via history and physical examination), and concomitant treatments (via assessment of concomitant medications).

If a subject experiences a prolonged QT interval  $> 500$  ms or of  $> 60$  ms over baseline the subject will discontinue the study and will be referred to their primary care provider for further evaluation (subjects must list a PCP to enroll in the study). If a subject experiences an adverse event suggestive of torsade de pointes, this will be treated as a medical emergency, upon which we will call 911 and the patient will be transported by ambulance to the University of Colorado Hospital emergency room. A significant adverse effect—myocardial ischemia or infarction, syncope, stroke, or seizure or other loss of consciousness, gastrointestinal blockage or severe diarrhea or emesis, or urinary retention, suicide attempt—will also lead to discontinuation of a subject. If any one of these criteria occurs in two subjects or a death in one subject while they

are being treated with DMXB-A, then the entire trial will be discontinued until the FDA, NIDDK, and the IRB, in conjunction with the investigators, have determined whether or not the trial should continue.

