Women who are capable of conception are excluded because the potential for teratogenicity of DMXB-A is not fully established. Incapable of conception is defined as post menopausal, surgical sterilization, or adherence to an anti-contraception birth control regimen (for at least 6 months if hormonal contraceptive). Women of child-bearing potential will be given a pregnancy test as part of screening procedures, at baseline, and on a monthly basis throughout the study. For this initial study, individuals who use nicotine, assessed by blood cotinine levels and self-report, will be excluded to preclude interactions between nicotine and the study drug. Subjects will be excluded for history of non-compliance in previous studies, and any form of nicotine use, including cigarettes, cigars, pipes, chewing tobacco, e-cigarettes, or nicotine gum. Medical history, physical examination, and blood screening tests (metabolic panel, lipid panel, complete blood count, TSH, A1c) will be performed to exclude for significant endocrine/metabolic disease (e.g., uncontrolled hypertension, severe hypertriglyceridemia, and diabetes) and kidney disease, neurological illness or injury that would be anticipated to affect subject safety or MRI data. UCH normal cutoff values will be used for exclusion criteria for blood screening tests for AST ( $> 39 \text{ U/L}$ ), ALT ( $> 52 \text{ U/L}$ ), TSH (0.5-5.0  $\mu\text{IU/mL}$ ), BUN ( $> 25 \text{ mg/dL}$ ), and Cr (M:  $> 1.3 \text{ mg/dL}$ ; F:  $> 1.2 \text{ mg/dL}$ ). Serum CR below UCH normal values ( $< 0.6 \text{ mg/dL}$  for women,  $< 0.7 \text{ mg/dL}$  for men) will

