(while following precautions that will include wearing a mask, gloves, and practicing appropriate social distancing). During each biweekly interaction, the side effects questionnaire and the Columbia Suicide Severity Rating Scale will be completed. Visits for weeks 2, 6, and 10 may be conducted virtually (via phone or video) to minimize the number of visits to campus. Vitals will be measured as part of screening measures, at baseline, and at weeks 4, 8, and 12. Physical exams will be conducted at screening, week 8 and week 12. Subjects will be evaluated further for any adverse event, with a physical exam if indicated. A clinical laboratory assessment including comprehensive metabolic panel, lipid panel, CBC, TSH, and A1c will be completed at screening. The comprehensive metabolic panel will be repeated at weeks 4, 8 and 12. The lipid panel will also be repeated at week 12. Leptin will be measured at screening and week 12. ECG monitoring will also be conducted every 4 weeks (screening and weeks 4, 8 and 12). Women of childbearing potential will complete urine pregnancy tests at screening, baseline, and monthly throughout the study (weeks 4, 8, and 12). As part of COVID-19-related precautions, we may take a measure of the participant's temperature at the beginning of each visit to campus. If they have a fever greater than 100.4 °F, the participant will be advised to seek medical care and the visit will be rescheduled for a later time. We will also use the most recent University COVID-19 screening questions to screen for COVID-19 symptoms/risk in advance of their scheduled visit and upon their arrival to campus. If the participant endorses any symptoms, has been in unprotected contact (within 6 feet for > 30 minutes) or caring for someone who has been diagnosed with COVID-19 within the last 30 days without wearing proper PPE, or has had a diagnosis of COVID-19 in the last 30 days, the visit will be rescheduled for a later time. If they endorse symptoms of COVID-19, they will be advised to seek medical care. Additionally, we will follow space plan guidelines and any instructions from COVID-19 officials regarding physical distancing and participant contact. Research staff and participants will be required to follow current University guidelines regarding PPE (e.g., wearing masks, gloves, face shields when necessary). If the participant will be traveling to campus via public transportation or cab/rideshare, they will be instructed to follow current University guidelines regarding PPE during transportation. Subjects enrolled in the study during the COVID-19 pandemic campus closure will be contacted via email to re-start the study if they are interested. Participants that are interested will be re-consented and informed of the changes made to the consent form. Since participants already passed the screening for the study, only safety measures including a CMP and ECG will be collected to ensure participants still qualify prior to repeating the baseline measures and intervention.

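### Blood pressure and heart rate have no on-treatment action level below a five-SD stop whose mean and SD are not named, so a symptom-free rise at week 4 need not be repeated or reviewed before week 8

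*Combined protocol and SAP*

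**What the plan says.** The individual stopping rules are in section IV, under Plans to Minimize Risk (DMXB-A). That text states "The stopping criteria are well defined" and then discontinues a subject for "any laboratory or vital sign value that is over five standard deviations from the mean", or for a significant finding on physical examination. The next tier down is confined to laboratory tests: "Changes over two times normal in laboratory values will be followed up immediately with repeat assessment", with the subject stopped if the change persists. Transaminases have a detailed ladder in multiples of the upper limit of normal. For QT, the limit is an interval above 500 ms, or more than 60 "ms over baseline the subject will discontinue the study and will be referred to their primary care provider for further evaluation".

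Section IV.B names a reference for the laboratory entry limits ("UCH normal cutoff values will be used for exclusion criteria for blood screening tests"). It also excludes uncontrolled hypertension, defined as above 150/95 mm Hg. That figure is not used again after entry.

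The schedule is in the section on description, risks and justification of procedures: "Vitals will be measured as part of screening measures, at baseline, and at weeks 4, 8, and 12" and "Physical exams will be conducted at screening, week 8 and week 12". ECGs are done at screening and at weeks 4, 8 and 12. A side-effects questionnaire is completed at each biweekly contact, and the contacts at weeks 2, 6 and 10 may be remote.

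**The concern.** The same section on risks names cardiovascular toxicity as a risk of nicotinic agonists in general, and section IV.B gives the cardiovascular effects of the class as the reason for the upper age limit. Subjects are overweight or obese and may enter with a pressure up to 150/95. Blood pressure and heart rate are therefore the measurements where one would expect a clear level for action.

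The protocol gives one numeric rule for them. It cannot be converted to mm Hg or beats per minute from the text, and nothing beneath it says what staff must do with a raised reading. A missing definition alone would be a drafting detail. The practical problem is the missing lower tier: a reading that would have kept the person out of the trial requires no repeat and no physician's review once dosing has begun.

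**Working it through.** **1. The rules side by side** (from Plans to Minimize Risk, DMXB-A)

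| Measurement | Lower tier | Numeric stop | Reference given |
|---|---|---|---|
| Laboratory values, general | Over 2 times normal: repeat at once, stop if it persists | Five SD from the mean | Normal, for the lower tier only |
| ALT, AST | Over 3 times ULN: repeat within 48 to 72 hours, then close observation | For example, over 8 times ULN, or over 5 times ULN for more than 2 weeks | ULN |
| QT | None | Over 500 ms, or over 60 ms above baseline | Absolute value and own baseline |
| Blood pressure, heart rate | None | Five SD from the mean | None |

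The fever rule (above 100.4 °F) is a COVID-19 precaution that reschedules a visit. It is not a stopping rule.

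**2. Can the five-SD limit be computed?** The upper limit is mean + 5 × SD. The documents give neither input, so there is no figure to reproduce. The following is illustration only, with an assumed systolic mean of 125 mm Hg:

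| Assumed SD | Upper stop | Entry limit of 150 in SDs | A reading of 180 in SDs | Does 180 stop the subject? |
|---|---|---|---|---|
| 10 | 125 + 50 = 175 | 25/10 = 2.5 | 55/10 = 5.5 | Yes |
| 15 | 125 + 75 = 200 | 25/15 = 1.7 | 55/15 = 3.7 | No |
| 20 | 125 + 100 = 225 | 25/20 = 1.25 | 55/20 = 2.75 | No |

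Two things follow. Whether 180 mm Hg stops a subject depends on an SD that the protocol does not state. In all three rows there is a band between 150 and the stop (25, 50 or 75 mm Hg wide) in which no repeat or review is required.

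The source of the mean and SD matters too. If they come from a set of n readings that includes the value being tested, the largest possible deviation is (n − 1)/√n sample SDs. For one subject's five scheduled readings this is 4/√5 = 1.79. For n = 26 it is 25/√26 = 4.90, and for n = 27 it is 26/√27 = 5.004.

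**3. How long can a raised reading stand?** This step uses only the documents.

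- On-treatment vital signs: weeks 4, 8 and 12.
- On-treatment physical exams: weeks 8 and 12, so week 4 has none.
- Week 6 contact: may be remote, with no vital signs scheduled.
- Dosing: one capsule a day. Week 4 to week 8 is 4 × 7 = 28 doses, out of about 12 × 7 = 84.
- Week 12: the last capsule is taken that morning, so this reading can spare at most one dose.

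Weeks 4 and 8 are therefore the readings that can still change dosing in a useful way. Week 8 is paired with a physical exam and its discretionary stop. Week 4 is not.

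**The case against.** The strongest reply is that the protocol is not silent in practice. Any adverse event must be evaluated further, with an exam if indicated. Investigators are in contact with subjects every two weeks. A significant exam finding is a stop in its own right, and exams accompany the vital signs at weeks 8 and 12. ECGs are done at weeks 4, 8 and 12, and ischemia, syncope and stroke are stopping events. Known cardiovascular disease, uncontrolled hypertension and age over 65 are excluded. The cardiovascular warning is about the class; for DMXB-A itself the protocol reports no significant preclinical ECG changes, and the signal it describes is in liver enzymes. Detailed tiers for liver tests are reasonable on that record.

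Most of this stands, and it narrows the gap to a symptom-free rise, mainly at week 4, that nobody chooses to record as an adverse event. It does not close the gap, because these safeguards are discretionary or respond to events, and none is tied to a blood pressure or heart-rate value.

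A reader might infer three stronger things that the documents do not support:

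- **That the five-SD stop is always too high to be useful, or can never fire.** At an assumed SD of 10 the systolic stop is 175 mm Hg, which is usable. The bound of 1.79 SD applies only if the reference is the subject's own five readings, which the text does not say.
- **That raised pressures would go unattended.** The text does not require a response, but neither does it prevent one.
- **That DMXB-A raises blood pressure.** The protocol reports no such finding.

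**Conclusion.** The point holds as a gap in the safety rules, and closing it is a cheap improvement. The only numeric on-treatment stop for vital signs is five SD from an unspecified mean, and no lower blood pressure or heart rate requires a repeat or review, unlike the rules for laboratory values and QT.

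The size that rests on the documents is the interval: a symptom-free pressure above the trial's own entry limit at week 4 need not be acted on for four weeks, about 28 daily doses. No mm Hg figure for the stop should be taken as a measure of the problem, since every such figure depends on an assumed mean and SD. The conclusion assumes that staff follow the text as written and that the reading brings no symptoms or other event that would trigger the existing safeguards.

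**What to change.** Keep the five-SD rule as a backstop for other vital signs, and state which mean and SD it uses. For blood pressure, add wording such as: any on-treatment reading above 150 mm Hg systolic or 95 mm Hg diastolic will be repeated promptly and reviewed by a study physician, who will hold or stop dosing if the elevation persists. For heart rate, the sponsor should set absolute or change-from-baseline limits, with the same repeat and review. The documents give no heart-rate figure from which to propose a value.

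This follows the repeat-then-stop pattern already used for laboratory values and the absolute or change-from-baseline form already used for QT. It relies on readings already scheduled and on study physicians to whom the protocol already assigns clinical judgements.

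The cost is a protocol wording change and a few extra repeat readings, physician reviews or stops, chiefly in subjects who enter just under 150/95 and cross it through ordinary variation. The repeat reading is there to limit stops of that kind. The number of extra readings cannot be estimated, because the documents give no blood pressure distribution.

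### For a transaminase elevation confirmed above 3x ULN that meets no listed liver criterion, the protocol gives two unreconciled instructions: stop the subject, or start close observation

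*Combined protocol and SAP*

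**What the plan says.** The individual stopping rules are in the DMXB-A part of Plans to Minimize Risk. Two of them reach ALT and AST.

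- **General laboratory rule.** "Changes over two times normal in laboratory values will be followed up immediately with repeat assessment". Then: "If the change persists, the subject will be stopped".
- **Transaminase rule.** A value above 3x ULN is repeated within 48 to 72 hours. If the repeat is still above 3x ULN, "close observation will be initiated to determine whether abnormalities are improving or worsening". Testing is then twice a week, and "Frequency of retesting can decrease to one per week or less if abnormalities stabilize". Two routes lead to stopping. The first is practical: "If close monitoring is not possible, the subject will discontinue the drug and stop the study". The second is a list of four criteria: above 8x ULN; above 5x ULN for more than 2 weeks; above 3x ULN with raised bilirubin or INR; above 3x ULN with named symptoms or eosinophilia.

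A later paragraph of the same part deals with continuing elevation during observation: "If elevated levels persist, we will rule out acute viral hepatitis", along with other causes. It does not mention stopping.

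Section IV.B excludes people with ALT above 52 U/L or AST above 39 U/L at screening. Section IV.C schedules the metabolic panel at weeks 4, 8 and 12.

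**The concern.** ALT and AST are laboratory values, so the general rule covers them on its face. The transaminase rule gives a different action for the same finding, and no sentence says that one displaces the other. Two study physicians who both follow the protocol could reach different decisions on the same result: one stops the subject, the other keeps the subject under observation.

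The first thing at stake is consistent handling of a liver signal that Section IV.D itself discusses at some length. There may also be an effect on the data. If *stopped* in the general rule means leaving the study, a result from the week 4 or week 8 panel could cost the post-intervention scan, which carries the primary outcome. The week 12 panel is drawn on the scan day, so it matters less here.

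**Working it through.** The plan gives no figure to reproduce. The check applies both rules to the same result.

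**Inputs.** ULN is not given a number for on-treatment testing. The screening cutoffs in Section IV.B (ALT 52, AST 39 U/L) are taken as ULN; this is an assumption.

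**Step 1: thresholds in U/L.**

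| Multiple | ALT | AST |
|---|---|---|
| 2x | 2 × 52 = 104 | 2 × 39 = 78 |
| 3x | 3 × 52 = 156 | 3 × 39 = 117 |
| 5x | 5 × 52 = 260 | 5 × 39 = 195 |
| 8x | 8 × 52 = 416 | 8 × 39 = 312 |

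**Step 2: does a value above 3x ULN always trigger the general rule?** The phrase about two times normal can be read in three ways. An eligible participant starts at or below 52 (ALT) or 39 (AST).

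- Level above 2x ULN: 156 exceeds 104, and 117 exceeds 78.
- Rise of more than 2x ULN from screening: the rise exceeds 156 − 52 = 104, or 117 − 39 = 78.
- More than double the screening value: the ratio exceeds 156/52 = 3, or 117/39 = 3.

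All three readings trigger the rule.

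**Step 3: the rules side by side.** Here persistence is judged at the repeat, no bilirubin, INR, symptom or eosinophilia criterion is met, and close monitoring is possible.

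| Confirmed ALT or AST | General rule | Transaminase rule |
|---|---|---|
| Above 3x to 5x | Stop | Observe; no duration-based stop stated |
| Above 5x to 8x | Stop | Observe; stop once above 5x for more than 2 weeks |
| Above 8x | Stop | Stop |

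The conflict runs from above 156 to 416 U/L for ALT and from above 117 to 312 U/L for AST. For example, an ALT of 200 U/L (200/52 = 3.85x) at week 4 and again on repeat is stopped under one rule and observed under the other.

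**Step 4: a longer meaning of *persists*.** If it means more than 14 days, a value that stays above 5x is stopped by the duration criterion as well, so the conflict above 260 (ALT) or 195 (AST) goes away. Between 3x and 5x the transaminase rule offers no matching criterion. Whether a stable value there is stopped or stays under observation is not settled.

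**Step 5: what follows if one rule is assumed to prevail.**

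- If the general rule applies at the repeat, 48 to 72 hours (2 to 3 days) is well short of 14 days. The criterion of more than 5x for more than 2 weeks then has almost no effect. The stop for subjects who cannot be closely monitored is also redundant, because it too follows a repeat above 3x.
- If the transaminase rule displaces the general rule only above 3x, and *normal* means ULN, a persistent ALT of 130 (2.5 × 52) is stopped while 200 is observed. On the rise reading, 130 triggers a stop only if the screening value was below 130 − 104 = 26 U/L.

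Neither assumption leaves the section consistent.

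**The case against.** The best reply is that the rules can be read in sequence: repeat, observe the trend, then stop if the change is finally judged to persist. The liver list says the subject stops if any criterion is met; it does not say only if. The sentence on less frequent retesting is permissive and does not mention dosing. This stands to a point. It rules out the tempting claim that the rules conflict between 3x and 5x on every definition of *persists*. But the protocol does not state the sequence, and its one sentence on persisting elevation under observation prescribes a work-up and no stop.

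A second reply is that a specific rule placed after a general one is normally read as the exception. A reader might infer from the reason given for the 3x threshold, "as lesser elevations are common and nonspecific", that the transaminase pathway was meant to govern. No sentence says so, and which clinical rule should govern is not a question for this review.

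A third reply is that the practical reach is small. Section IV.D reports elevations to 5 times normal in several subjects of a volunteer study, placebo recipients among them. It reports nothing similar in Phase 1, and Phase 2 elevations that rarely passed 3 times normal and were gone on retest. The disputed case needs a confirmed elevation. The symptom criterion includes nausea, which Section IV.D names as a chief symptom, so some participants would leave the disputed band. Under either rule a confirmed elevation above 3x is retested promptly, so the dispute is about stopping, not about whether anyone is watching. All of this stands, and it limits how large the problem can be said to be. It does not remove the contradiction.

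**Conclusion.** The concern holds within stated limits. For a transaminase still above 3x ULN on repeat, with no listed liver criterion met and close monitoring possible, the protocol gives two instructions and no way to choose between them. With persistence judged at the repeat, which is the natural reading, the conflict covers values above 3x and up to 8x ULN. With persistence meaning more than 14 days, only the range from 3x to 5x remains, and there the outcome is unresolved unless the rules are read in sequence. The U/L figures rest on taking the screening cutoffs as ULN.

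Some stronger readings are not supported.

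- A reader might infer an unconditional conflict across the whole 3x to 8x range; above 5x it depends on what *persists* means.
- A reader might infer that a participant would lose the scan a set number of days early. That would need exact visit days, a 12-week course that the protocol calls approximate, and a meaning of *stopped* that the general rule does not give.
- A reader might count the rule on "any laboratory or vital sign value that is over five standard deviations from the mean" as a third contradiction. Its mean and SD are not named, so it is missing detail rather than a shown conflict.

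The documents do not allow the number of affected participants to be stated.

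**What to change.** Reconcile the two paragraphs in the DMXB-A part of Plans to Minimize Risk. State which rule applies to transaminases, including values between 2x and 3x ULN, and which applies to other laboratory values. State when a change counts as persisting. In the same edit, say what *normal* refers to and whether *stopped* means stopping the drug or leaving the study. The thresholds and actions are for the sponsor and regulators to choose. The cost is the wording of a protocol amendment; no visit, test or sample size has to change for the text to be made consistent.

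### INR and eosinophils can each trigger a liver stop, but the tests listed for participants above 3 times ULN include neither

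*Combined protocol and SAP*

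**What the plan says.** All of the relevant rules are in the DMXB-A part of Plans to Minimize Risk.

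- **Repeat test.** A transaminase value above 3 times ULN "will be followed by repeat testing of ALT, AST, ALP, and TBL within 48 to 72 hours".
- **Close observation.** If the repeat is still above 3 times ULN, "Close observation will include repeating liver enzyme and bilirubin tests 2 times per week". The rate may fall later: "Frequency of retesting can decrease to one per week or less if abnormalities stabilize". The work-up adds disease history, a medication review, exposure history and "ruling out acute viral hepatitis types A, B, C, D, and E, autoimmune or alcoholic hepatitis, and cardiovascular disease". A following paragraph says that these causes are to be excluded by serology, history and examination.
- **Liver stopping criteria.** There are four. The third combines a value above 3 times ULN with either bilirubin (TBL) above 2 times ULN or INR above 1.5. The fourth combines it with any of a list that starts with fatigue, nausea and vomiting and ends with "right upper quadrant pain or tenderness, fever, rash, and or eosinophilia", the last set at more than 5%.
- **General rules.** A laboratory change of more than twice normal is retested at once, and "If the change persists, the subject will be stopped". Separately, "any laboratory or vital sign value that is over five standard deviations from the mean" leads to discontinuation.

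Scheduled on-treatment liver monitoring is a metabolic panel at weeks 4, 8 and 12. A CBC is scheduled at screening.

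**The concern.** A stopping rule can be applied reliably only if the plan says which test supplies each of its inputs, and when. Here the same section sets INR and eosinophil limits and then lists event-driven tests that produce neither value. The protocol joins both limits to the other triggers as alternatives, so each is meant to stop a participant even when bilirubin is acceptable and symptoms are absent.

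At stake is the safety of a participant under close observation. The pathway implies continued dosing, because it withdraws drug only if monitoring is not possible or a criterion is met. If a site ran the listed tests and nothing more, a raised INR or eosinophil percentage in that participant would go unseen. Outcomes and analysis are not affected.

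**Working it through.** No figure in the plan needs reproducing. The check sets criteria against tests, then sizes the range affected.

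**1. Inputs against listed tests.** The listed tests are ALT, AST, ALP and TBL at the repeat, then liver enzymes and bilirubin.

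| Liver stopping criterion | Laboratory inputs | Without a listed test |
|---|---|---|
| Above 8x ULN | ALT, AST | none |
| Above 5x ULN for more than 2 weeks | ALT, AST | none |
| Above 3x ULN, with TBL above 2x ULN or INR above 1.5 | ALT, AST, TBL, INR | INR |
| Above 3x ULN, with symptoms and/or eosinophilia above 5% | ALT, AST, eosinophils | eosinophils |

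There are five distinct inputs (ALT, AST, TBL, INR, eosinophils). Three have a listed test and two do not. The two fall in 2 of the 4 criteria.

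**2. Could another part of the plan supply them?** INR and eosinophilia appear nowhere in the text except in these criteria. The metabolic panels are not described as including either. The screening CBC precedes treatment. Blood Analyses also mentions a CBC at the first draw of the post-intervention day, but names no differential, and only the final capsule follows that draw. It cannot guide stopping during treatment.

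**3. The range left to close observation.** This takes the upper cutoffs in Description of Population to be Enrolled as ULN (ALT 52 U/L, AST 39 U/L).

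- ALT: 3 × 52 = 156; 5 × 52 = 260; 8 × 52 = 416 U/L.
- AST: 3 × 39 = 117; 5 × 39 = 195; 8 × 39 = 312 U/L.

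Without another trigger, observation can continue with no time limit above ALT 156 and up to 260 U/L, or above AST 117 and up to 195 U/L. It can continue for up to 2 weeks at values up to 416 or 312 U/L.

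**4. Overlap with the general rule.** Twice ULN is 2 × 52 = 104 U/L for ALT and 2 × 39 = 78 U/L for AST, both below the 3-times thresholds. Reading the rule as a rise from baseline gives the same answer. Entry requires ALT no higher than 52 and AST no higher than 39, so a value above 156 or 117 is a rise of more than 156 − 52 = 104 or 117 − 39 = 78. On either reading, a persistent value above 3 times ULN also meets the general rule, if that rule covers transaminases.

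**5. How many draws would carry the extra assays.** Twice-weekly testing starts after the 2 to 3 day repeat. A rise found at week 4 leaves 56 − 3 = 53 to 56 − 2 = 54 days before week 12. That is about 7.6 to 7.7 weeks, or about 15 draws plus the repeat. A rise found at week 8 leaves 25 to 26 days, or about 7 draws plus the repeat. Fewer follow if retesting slows.

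**The case against.** The case on the other side is substantial, and most of it stands.

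- **The tests are not forbidden.** The lists say what observation will include, and a participant stops once a criterion is determined, which implies that someone must determine it. Participants are also to be evaluated further for any adverse event. A reader might infer that the INR and eosinophil triggers can never be met. The documents do not support that. They show only that the test and its timing are unstated.
- **Both inputs are alternatives.** INR stands beside TBL, which is tested at the repeat and during observation. Eosinophilia stands beside six symptoms or signs, and side effects are asked about at each biweekly contact. A reader might take two of the four criteria to be disabled, but none is.
- **Few should reach the pathway.** The section on risks and justification of procedures reports that Phase 2 elevations seldom exceeded three times normal, were as frequent on placebo, and were absent on repeat testing. Close observation needs a persistent elevation. Against this, the same section reports rises to five times normal in several volunteers in another study, including some on placebo. The pathway may therefore be entered, but this is no evidence of drug toxicity.
- **The general rule may stop these participants anyway.** If it covers transaminases, the missing inputs are irrelevant to stopping. The protocol justifies 3 times ULN by calling smaller rises common and nonspecific, and it sets up twice-weekly testing, so the liver pathway is probably meant to govern. The text does not say so. The five-standard-deviation rule might also act, but its mean and standard deviation are not defined and no threshold can be derived.
- **A procedures table is cited under Blood Analyses** but is not in the text available. It could list more tests.

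**Conclusion.** The concern holds in a narrow form. Two of the four liver stopping criteria include an alternative laboratory trigger that is absent from the tests listed for participants above 3 times ULN. The consequence is limited to a participant kept on drug with persistent ALT or AST above 3 times ULN, TBL not above 2 times ULN and none of the listed symptoms. The number of such participants cannot be computed from the documents, and the Phase 2 account suggests it will be small.

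This rests on two assumptions: that the specific liver pathway takes precedence over the twice-normal rule for transaminases, and that the procedures table does not already supply the tests. The ranges in U/L also assume that the enrolment cutoffs are the ULN. This is a worthwhile, inexpensive improvement to the safety wording. It is not a failure of liver monitoring as a whole.

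**What to change.** Make two changes in the DMXB-A part of Plans to Minimize Risk.

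1. Add INR and a CBC with differential to the 48 to 72 hour repeat testing and to the tests repeated during close observation.
2. State that, for transaminases, the pathway for values above 3 times ULN replaces the general rule on changes of more than twice normal. Without this sentence, the added tests may have no bearing on stopping.

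The cost is two extra assays per draw, on draws already planned and only for participants above 3 times ULN. At most this is about 16 draws for a participant identified at week 4, or about 8 for one identified at week 8. No visits are added, and outcomes and analysis do not change.
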